8.5 Study Population with inclusion and exclusion criteria

Five non-mutually exclusive study cohorts for the analyses will be defined:

- 1. General population cohort for pre-pandemic background rates** will have
 - Individuals will start contributing as of 1st January 2017, or when they have at least 365 days of data availability.
 - follow-up for this cohort will run up to 31 December 2019.
- 2. Persons tested positive for SARS-CoV-2 or with a clinical diagnosis of COVID-19 during the Omicron period** will
 - have either a positive test result for SARS-CoV-2 or a clinical diagnosis of COVID-19 on or after 1st December 2021 (with the index date being whichever date comes first if both occur)
 - have no positive test result for SARS-CoV-2 or clinical diagnosis of COVID-19 within 3 months prior to the index date.
 - have at least 365 days of data availability prior to index date
- 3. Persons hospitalised with COVID-19 during the Omicron period** will have
 - a hospitalisation on or after 1st December 2021 (with the index date the date of hospital admission),
 - a record of a clinical diagnosis of COVID-19 or a positive test result for SARS-CoV-2 in the period between 3 weeks prior to and up to 3 days following the index date.
 - have no diagnosis of COVID-19 or a positive test result for SARS-CoV-2 between 3 months and 3 weeks prior to index date.
 - have no COVID-19 hospitalisation within 3 weeks prior to the index date.
 - have at least 365 days of data availability prior to index date
- 4. Persons requiring intensive services during a hospitalisation with COVID-19 during the Omicron period** will have
 - intensive services initiated during a hospitalisation as described in cohort 3 (with the index date the date at which intensive services were initiated)
 - patients will have had a confirmatory diagnosis or test result of COVID-19 (both as defined above) within a time window from 3 weeks to their index date up to three days following their index date.
 - have at least 365 days of data availability prior to index date
- 5. Persons vaccinated against SARS-CoV2 infection**
 - a vaccination record identified by brand (with the index date the date of vaccination record)

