 - whether the vaccination record is 1st, 2nd, 3rd or 4th dose. A 21 day gap between two consecutive records of vaccine will be required to avoid repeated records of the same vaccine. The 21-days period was chosen based on the minimal recommended dosing schedule of the primary vaccine course in participated databases (Spain).
 - have at least 365 days of data availability prior to index date

Cohorts 2 to 5 will be stratified by prior COVID-19 infection status and for cohorts 2 to 4 also by prior SARS-CoV-2 vaccination status. All cohorts will additionally be stratified by whether patients are immunocompromised on the index date. People in each of the five cohorts will be required to have at least a year of observed history in the database prior to their index date. This is to ensure a sufficient time period to identify health conditions and medication use prior to individuals' index dates.

	Phase II C3-001 – Study Protocol	
	Author(s): [name], [name]	Version: v3.1
		Dissemination level: public

Table 3. Operational Definitions of Inclusion Criteria

Criterion	Details	Order of application	Assessment window	Care Setting ¹	Code Type	Diagnosis position ²	Applied to study populations:	Measurement characteristics/validation	Source for algorithm
Observation period of 365day prior entry (all 5 cohorts)	Study participants will be required to have 365 days prior history observed before contributing observation time	before	[-365,0]	n/a	n/a	n/a	All individuals within the selected databases	n/a	n/a
Covid-19 infection (cohort 2)	have either a positive test result for SARS-CoV-2 or a clinical diagnosis of COVID-19 on or after 1 st December 2021 (with the index date being whichever date comes first if both occur)	before	n/a	Primary care	SNOMED	n/a	All individuals within the selected databases	n/a	n/a
Covid-19 hospitalized (cohort 3)	a hospitalisation on or after 1 st December 2021 (with the index date the date of hospital admission), a record of a clinical diagnosis of COVID-19 or a positive test result for SARS-CoV-2 in the period between 3 weeks prior to and up to 3 days following the index date	before	[-21, 3]	Primary care, secondary care	SNOMED	n/a	All individuals within the selected databases	n/a	n/a

	Phase II C3-001 – Study Protocol	
	Author(s): [name], [name]	Version: v3.1
	Dissemination level: public	

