Covid-19 intensive care use (cohort 4)	intensive services initiated during a hospitalisation as described in the “covid-19 hospitalized” criterion	before	During hospitalization	Intensive care	SNOMED	n/a	Individuals who met the “covid-19 hospitalized” criteria	n/a	n/a
Covid-19 vaccinated (cohort 5)	a vaccination record identified by brand (with the index date the date of vaccination record)	before	n/a	Primary care	RxNorm	n/a	All individuals within the selected databases	n/a	n/a

¹ IP = inpatient, OP = outpatient, ED = emergency department, OT = other, n/a = not applicable

² Specify whether a diagnosis code is required to be in the primary position (main reason for encounter)

Table 4. Operational Definitions of Exclusion Criteria

Criterion	Details	Order of application	Assessment window	Care Setting¹	Code Type	Diagnosis position²	Applied to study population^s	Measurement characteristic^{s/}	Source for algorithm
Prior covid-19 (cohort 2-4)	have no positive test result for SARS-CoV-2 or clinical diagnosis of COVID-19 within 3 months prior to the index date.	After	[-91,0]	OP,IP	SNOMED, RxNorm	n/a	SARS-CoV-2 infected, hospitalized (cohorts 2, 3, 4)	n/a	n/a

	Phase II C3-001 – Study Protocol	
	Author(s): [name], [name]	Version: v3.1
	Dissemination level: public	

Hospitalization (cohort 3)	have no diagnosis of COVID-19 or a positive test result for SARS-CoV-2 between 3 months and 3 weeks prior to index date. Have no COVID-19 hospitalisation within 3 weeks prior to the index date.	After	Covid-19 [-91,-21]; Hospitalization [-21,0]	IP	SNOMED	n/a	Covid-19 hospitalized (cohorts 3, 4)	n/a	n/a
Vaccinated (cohort 5)	No vaccine records in the 21 days prior to index vaccine	after	[-21 , 0]	OP	RxNorm	n/a	Vaccinated (cohort 5)	n/a	n/a
Prior outcomes all cohorts)	Exclude people with the outcome of interests during the 183 day prior to index. (primary analysis, different washout period will be applied in sensitivity analysis)		[-183,0]	IP, OP	SNOMED	n/a	(cohorts 1-5)	n/a	n/a

1 IP = inpatient, OP = outpatient, ED = emergency department, OT = other, n/a = not applicable

2 Specify whether a diagnosis code is required to be in the primary position (main reason for encounter)

Criterion: A brief text entry naming the in- and/or exclusion criterion (e.g. age, sex, atrial fibrillation)

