Details: An optional brief text description to provide more information about the in- and/or exclusion criterion (e.g. age in years defined by (time 0 – year of birth)/365, baseline enrolment measured by Part A, B, D and no HMO insurance coverage with 30 day gaps allowed), 2 codes required

	Phase II C3-001 – Study Protocol	
	Author(s): [name], [name]	Version: v3.1
		Dissemination level: public

Order of application: Specify whether the in and exclusion criterion is applied before or after selection of the study entry date. For example, enter “before” if you plan to apply the criterion, identify all possible study entry dates, and then choose one or more. Enter “after” if you select the first possible study entry date and then apply the in- and/or exclusion criterion. If the patient does not meet the criterion, then the patient drops out. These decisions can impact which samples of person-time are included in the study.

Assessment window: Use bracketed numbers representing time intervals anchored on a primary anchor (usually time 0) to specify the window over which to evaluate patient data relevant for the in- and/or exclusion criterion. For example, [-180, 0] would reflect an assessment window of 180 days prior to and including time 0, where the brackets indicate that the window is inclusive of the endpoints.

Care setting: Specify the care setting(s) that are used in the algorithm to define the in- and/or exclusion criterion. For example, IP = inpatient, ED = emergency department, etc.

Code type: Specify the type(s) of clinical codes that are used to define the in- and/or exclusion criterion.

Diagnosis position: If the algorithm to define the in- and/or exclusion criterion used inpatient codes, specify whether the algorithm restricts to primary diagnosis codes (indicating that the code is the primary reason for the encounter) or allows codes in secondary or any position (e.g. primary, secondary, any, n/a)

Applied to study populations: Indicate which study populations the in- and/or exclusion criterion should be applied to (study population names are specified in Table 2).

Measurement characteristics/validation: If there are measurement characteristics for the outcome algorithm (e.g. PPV, sensitivity, specificity) from publications, or from outcome validation within the study population (e.g., medical record review), provide this information.

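### Table 4's exclusion windows conflict with section 8.5 and with Tables 2, 5 and 6, most seriously by excluding cohorts 3 and 4 for the COVID-19 record they must have

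*Protocol*

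**What the plan says.** The notes under Table 4 fix the notation. A window ending in 0 runs "prior to and including time 0, where the brackets indicate that the window is inclusive of the endpoints". The same notes say that a criterion applied after the entry date is chosen removes a patient who fails it. The COVID-19, hospitalisation and vaccine rows of Table 4 are all marked that way.

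- **Prior COVID-19 (Table 4, first row).** People must "have no positive test result for SARS-CoV-2 or clinical diagnosis of COVID-19 within 3 months prior to the index date". The window is [-91,0] and the populations are "SARS-CoV-2 infected, hospitalized (cohorts 2, 3, 4").
- **Cohort 3 (section 8.5, Table 3).** Inclusion needs "a record of a clinical diagnosis of COVID-19 or a positive test result for SARS-CoV-2 in the period between 3 weeks prior to" admission, with the span closing three days after it. Section 8.5 bars COVID-19 records only from three months to three weeks before admission. Cohort 4 needs a record in the same 25-day span around the start of intensive services. Section 8.6.1 explains that the span is meant to bring in patients diagnosed before they were admitted.
- **Hospitalisation (Table 4, second row, cohorts 3 and 4).** COVID-19 records are barred in [-91,-21] and COVID-19 hospitalisation in [-21,0].
- **Vaccination.** Table 4 asks for "No vaccine records in the 21 days prior to index vaccine", window [-21,0]. Section 8.5 requires a 21-day gap between records, to screen out repeat entries of the same dose, and explains: "The 21-days period was chosen based on the minimal recommended dosing schedule of the primary vaccine course in participated databases (Spain").
- **Prior outcomes.** Table 4 says "Exclude people with the outcome of interests during the 183 day prior to index", window [-183,0]. Every row of Table 6 ends its washout at -1.
- **Hospitalisation washout.** Table 2 (cohort 3) and Table 5 give three months. Section 8.5 and Table 4 give three weeks.

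**The concern.** These tables are the operational definitions from which the cohorts will be programmed, and they disagree with the text they are meant to implement. For cohorts 3 and 4, the record that qualifies a patient is in most positions also the record that excludes the patient. Those who remain are people whose infection was first recorded after admission (cohort 3) or after intensive services began (cohort 4). That reverses the purpose stated in section 8.6.1.

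The effect reaches objective 4b. Its first transition, in section 8.8.4, runs from an outpatient diagnosis or positive PCR test to hospitalisation with COVID-19. If the hospitalised state is built from cohort 3 as Table 4 defines it, a patient with an outpatient record in the 91 days before admission is dropped, and that is the patient the transition describes. The objectives table says inpatient data exist only in SIDIAP, so no other database can compensate.

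The vaccine window bears on dose-specific rates in objectives 3 and 5. The outcome-washout and hospitalisation-washout conflicts are less visible: either version runs without error, and the versions can give different cohorts and different early event rates.

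**Working it through.** The Protocol states no figure to reproduce. The check enumerates days as closed integer intervals, following the Protocol's own bracket rule, with index day = 0.

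**1. COVID-19 record, cohorts 3 and 4.** Qualifying window [-21,+3]: 3 - (-21) + 1 = 25 days. Days that qualify and do not exclude:

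| Exclusion window | Overlap with [-21,+3] | Days left | Share of days lost |
|---|---|---|---|
| First row as written, [-91,0] | -21 to 0: 22 | +1 to +3: 3 | 22/25 = 88% |
| First row read as [-91,-1] | -21 to -1: 21 | 0 to +3: 4 | 21/25 = 84% |
| Second row as written, [-91,-21] | -21: 1 | -20 to +3: 24 | 1/25 = 4% |
| Second row repaired, [-91,-22] | none | -21 to +3: 25 | 0% |

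The conflict with the first row therefore does not depend on day 0. The share of patients lost is 1 - p, where p is the share whose first record falls on days +1 to +3 (0 to +3 on the second reading). The Protocol does not give p.

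**2. Hospitalisation window, second row.** In cohort 3 the index admission is day 0, which lies inside [-21,0]. Ending at -1 cures this for cohort 3. In cohort 4 day 0 is the start of intensive services, so a patient admitted 1 to 21 days earlier is still caught by [-21,-1] through their own admission. The look-back has to be anchored to the admission date.

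**3. Vaccine records.** A gap of g days places the previous dose at day -g. Is that dose inside the exclusion window?

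| Gap | [-21,0] | [-21,-1] | [-20,-1] |
|---|---|---|---|
| 20 days | yes | yes | yes |
| 21 days | yes | yes | no |
| 22 days | no | no | no |

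Section 8.5 accepts a 21-day gap. Table 4 rejects it on either reading of the end point. Only [-20,-1] matches section 8.5, and it still removes records 20 days apart or closer. Read literally, [-21,0] also contains the index dose.

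**4. Outcome washout.** An event on day 0 lies in [-183,0] but not in [-183,-1]. Under Table 4 the person is excluded; under Table 6 the event can be counted. Section 8.4 starts follow-up on the index date, which agrees with Table 6.

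**5. Hospitalisation washout.** Three months (Tables 2 and 5) against 21 days (section 8.5, Table 4). Table 2 also does not restrict the earlier admission to COVID-19, whereas section 8.5 does. A patient with a COVID-19 admission 22 to 91 days earlier passes one rule and fails the other.

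**The case against.** The best defence is that these are slips of notation. The prose of the first row speaks of records before the index date, and the objectives table bars any other vaccine record, so the index record was not meant to count. The Protocol uses 0 loosely elsewhere: immunocompromise is described as recorded before the index date in section 8.6.3 but has the window [-365,0] in Table 7. The second row of Table 4 also carries nearly the right COVID-19 rule for cohorts 3 and 4, so the first row may simply list too many cohorts.

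Much of this stands, and it rules out three stronger readings.

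- A reader might infer that cohort 2 would be empty, since its index record falls on day 0. That rests on the end point alone, the same row's prose contradicts it, and an empty cohort would show on the first run. Applied evenly, the same literalism would also empty cohorts 3 and 5, so it is better treated as an error to correct than as a forecast loss.
- A reader might infer that most hospitalised patients would be lost. The 84% to 88% is a share of days. The Protocol gives no timing of COVID-19 records around admission.
- A reader might scale the vaccine point by SIDIAP's 6,548,545 Pfizer feasibility records. The Protocol gives neither the split by dose nor the distribution of intervals, and calling 21 days a minimum does not say how many doses fall on that day.

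The defence does not reach the main conflict or the 21-day gap, because both persist when 0 is read as -1. The two washout conflicts are differences between tables that no reading of the prose settles. The planned run of CohortDiagnostics is described as a check on concept sets and cannot be relied on to expose a wrong window.

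**Conclusion.** The point holds, as a set of internal contradictions. The most serious is the first row of Table 4 applied to cohorts 3 and 4. It leaves 3 of 25 qualifying days as written, or 4 of 25 on the lenient reading, and it contradicts section 8.5, the purpose given in section 8.6.1, and Table 4's own second row. The number of patients affected is unknown. The effect on objective 4b assumes that the hospitalised state is drawn from cohort 3.

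The 21-day vaccine boundary, the day-0 difference between Tables 4 and 6, and the three-month against three-week hospitalisation washout are also real conflicts. None can be sized from the Protocol. On index-day outcomes, section 8.4 and Table 6 both lean towards counting them. The choice is the sponsor's, but the tables must agree. Until these entries are reconciled, two programmers could follow the Protocol and build different cohorts for objectives 2 to 5.

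**What to change.** - **Table 4, first row:** apply it to cohort 2 only, with window [-91,-1], since day 0 is the index record itself.
- **Table 4, second row, cohort 3:** COVID-19 records [-91,-22]; prior COVID-19 hospitalisation [-21,-1].
- **Cohort 4:** use the same look-backs anchored to the admission date, so that the patient's own index admission is never an exclusion.
- **Vaccine row:** set the duplicate-record window to [-20,-1]. This is a data-cleaning rule only.
- **Outcome washout:** state one rule in both Table 4 and Table 6, and run the other as a sensitivity analysis.
- **Hospitalisation washout:** reconcile Tables 2 and 5 with section 8.5 and Table 4, and say whether only COVID-19 admissions count.

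The cost is a short Protocol amendment plus the added sensitivity analysis, with no new data. The milestones give no date yet for the analytical code, so the change can be made before the cohorts are programmed.

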	
3. To estimate the incidence rate of venous and arterial thromboembolic events among patients with SARS-CoV-2 vaccination within 30-, 60-, 90- and 180-days, stratified by prior infection status.
 
4. To estimate a) the association between clinical risk factors, including prior SARS-CoV-2 vaccination, on the incidence rate of venous and arterial events among patients with COVID-19 and b) the impact that thromboembolic events have on worsening severity of COVID-19 during the Omicron period.
 
5. To estimate incidence rate ratios for venous and arterial thromboembolic events among patients with COVID-19 and different SARS-CoV-2 vaccine doses compared to the background population, using incidence rates estimated in objectives 1 to 3.

Hypothesis:	
Objective 1 – 3 are descriptive incidence rate, not applicable.
 
Objective 4: Some factors/ characteristics are associated with a) the incidence of venous and arterial thromboembolic events among patients with COVID-19 and b) worsening of COVID-19 during the period whenOMICRON was the dominant variant.
 
Objective 5: Being infected with Omicron variant or being vaccinated may be related to changes in the incidence rates of thromboembolic events.

Population (mention key inclusion-exclusion criteria):	
Objective 1: General population cohort for pre-pandemic background rates will have:
 
 • people included in the database as of 1 January 2017 or when they fulfil 365 days of prior history. • follow-up for this cohort will run up to 31 December 2019. 
Objective 2: Persons tested positive for SARS-CoV-2 or with a clinical diagnosis of COVID-19 during the Omicron period will:
 
 • have either a positive test result for SARS-CoV-2 or a clinical diagnosis of COVID-19 on or after 1st December 2021 (with the index date being whichever date comes first if both occur) • have no positive test result for SARS-CoV-2 or clinical diagnosis of COVID-19 within 3 months prior to the index date. 
Objective 3: Persons vaccinated against SARS-CoV2 infection:
 
 • a vaccination record identified by brand (with the index date the date of vaccination record) and not any other record of vaccine in the prior 21 days. The 21 days was based on the

	Phase II C3-001 – Study Protocol	
	Author(s): [name], [name]	Version: v3.1
	Dissemination level: public	

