COVID-19 vaccine exposure will be defined as the date of a vaccination record. Vaccination exposures will be defined by dose (1st, 2nd, 3rd, 4th etc.) and brand. The standard concepts used to define vaccine are available in the appendix.

Table 5. Operational Definitions of Exposure

Exposure group name(s)	Details	Washout window	Assessment Window	Care Setting ¹	Code Type	Diagnosis position ²	Applied to study populations:	Incident with respect to...	Measurement characteristics/validation	Source of algorithm
Positive test result for SARS-CoV-2	All positive test results for SARS-CoV-2 observable in the database. We will record the test type as well.	3 months	n/a	OP, IP	SNOMED	n/a	All meet observation period criteria	n/a	n/a	n/a
Clinical diagnosis of COVID-19	Diagnostic codes compatible with COVID-19 will therefore also be identified	3 months	n/a	OP, IP	SNOMED	n/a	All meet observation period criteria	n/a	n/a	n/a
Covid-19 hospitalization	having a hospitalisation along with a confirmatory diagnosis or test result of COVID-19 (both as defined above) within a time window from 21 days prior to admission up to three days following their admission.	3 months	n/a	IP	SNOMED		All meet observation period criteria	n/a	n/a	n/a
Covid-19 intensive care services	received intensive care services during a hospitalisation with COVID-19 will be identified based on having a hospitalisation where they were admitted to the intensive care unit, received mechanical ventilation,	n/a	During hospitalization	IP	SNOMED	n/a	All patient meet the covid-19 hospitalization criteria	n/a	n/a	n/a

	Phase II C3-001 – Study Protocol	
	Author(s): [name], [name]	Version: v3.1
	Dissemination level: public	

	tracheostomy, or extracorporeal membrane oxygenation (ECMO).									
Vaccination against SARS-CoV-2	COVID-19 vaccine exposure will be defined as the date of a vaccination record. Vaccination exposures will be defined by dose (1 st , 2 nd , 3 rd , 4 th etc.) and brand.	21 days	n/a	OP	SNOMED	n/a		n/a	n/a	n/a

¹ IP = inpatient, OP = outpatient

² Specify whether a diagnosis code is required to be in the primary position (main reason for encounter)

Criterion: A brief text entry naming the in- and/or exclusion criterion (e.g. age, sex, atrial fibrillation)

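### The 21-day repeat-record rule for vaccine doses is applied after entry selection and measured from any earlier record, so a repeat entry can remove a genuine dose from its dose cohort

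*Protocol*

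**What the plan says.** Section 8.5 (cohort 5) gives the purpose of the rule: "A 21 day gap between two consecutive records of vaccine will be required to avoid repeated records of the same vaccine". The same bullet makes dose number a cohort attribute ("whether the vaccination record is 1st, 2nd, 3rd or 4th dose") and ties the 21 days to the shortest primary-course schedule among the participating databases.

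Table 4 puts the rule into operation as an exclusion: "No vaccine records in the 21 days prior to index vaccine", window [-21, 0], order *after*. The notes below the table say that *after* applies "if you select the first possible study entry date and then apply the in- and/or exclusion criterion", and add: "If the patient does not meet the criterion, then the patient drops out". Bracketed windows are described with the words "where the brackets indicate that the window is inclusive of the endpoints".

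The objectives table in Section 7 makes the gap a condition on the record: "not any other record of vaccine in the prior 21 days". Tables 2 and 5 list 21 days as the washout, and Table 2 allows multiple entries for this cohort. Section 8.6.1 states: "Vaccination exposures will be defined by dose (1st, 2nd, 3rd, 4th etc.) and brand".

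**The concern.** A rule meant to remove duplicates should discard the repeat record and leave the real doses alone. Table 4 does something else, in two respects.

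- **Order.** The entry date is picked first and the entry is lost if it fails. The repeat is not cleaned out of the record sequence beforehand.
- **Anchor.** Sections 7 and 8.5 and Table 4 all measure the gap from any preceding vaccine record. None measures it from the last accepted dose, so a rejected repeat can still disqualify the genuine dose that follows it.

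Dose number is at stake because it defines the exposure. Objective 5 compares different vaccine doses with the background population. Section 11 says that primary courses went to the general population and 4th doses to more vulnerable people, so dose cohorts with wrong labels mix different risk profiles. Section 11 also assumes that vaccination recording is complete, and none of the sensitivity analyses in Table 9 varies this rule.

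**Working it through.** The protocol states no figure on this point, so there is none to reproduce. The check follows record sequences through the rule.

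**Inputs from the protocol:** no other vaccine record in [-21, 0], endpoints included; order *after*; gap counted from any earlier record.

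**Assumed for illustration:** dose 1 on day 0; one repeat of it on day r, with r = 1 to 20; true dose 2 on day s; dose 3 on day s + 180; dose 4 on day s + 360.

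**1. One sequence: days 0, 10 and 25.**
- Against the previous true dose: 25 − 0 = 25 > 21, passes.
- Against the repeat: 25 − 10 = 15 ≤ 21, fails.

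The genuine dose 2 is excluded because of the repeat alone.

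**2. How often dose 2 survives.** It survives only if s − r > 21, that is r ≤ s − 22. Out of 20 lags, the number that survive is min(20, max(0, s − 22)).

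| Dose 2 on day s | s − 22 | Lags at which dose 2 survives |
|---|---|---|
| 21 | −1 | 0 of 20 |
| 28 | 6 | 6 of 20 |
| 42 | 20 | 20 of 20 |
| 84 | 62 | 20 of 20 |

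At s = 21 the inclusive window excludes dose 2 even without a repeat, since 21 − 0 = 21 lies inside it. That is a separate boundary question.

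**3. What happens to dose numbers.** With s = 25, dose 3 falls on day 205 and dose 4 on day 385.

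| Record | Number raw records, then apply gap | Apply gap to any earlier record, then number | Collapse against last retained dose, then number |
|---|---|---|---|
| Day 0, dose 1 | 1st | 1st | 1st |
| Day 10, repeat | counted 2nd, excluded | dropped | dropped |
| Day 25, dose 2 | counted 3rd, excluded | dropped | 2nd |
| Day 205, dose 3 | **4th** | **2nd** | 3rd |
| Day 385, dose 4 | 5th record | **3rd** | 4th |

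The first two procedures both lose dose 2 and mislabel what follows, in opposite directions. The third keeps every label, and does so at every repeat lag tested when s is 22 or more.

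**4. Changing the order alone is not enough.** The middle column already removes failing records before numbering, yet it loses the day-25 dose. The anchor has to change as well.

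**5. A longer distance from the repeat.** With days 0, 5 and 28, 28 − 5 = 23 > 21, so dose 2 passes. It is then labelled 2nd if the gap comes first, and 3rd if raw records are numbered.

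**The case against.** The strongest reply is that the protocol can be read as removing repeats first. Section 7 makes the gap a condition for a record to qualify and only then turns to dose number. Section 8.5 puts the gap and its purpose inside the dose-number bullet. Tables 2 and 5 call it a washout. On that reading a day-5 repeat is never dose 2, and nothing shifts upward. The explanation of *after* is also template guidance for filling in a column, and the details of dose counting may sit in an analysis plan or code that is not shown.

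Much of this stands. A reader might infer that true 2nd and 3rd doses move up into the 3rd- and 4th-dose cohorts. The documents do not support that as a flat statement. It needs numbering on raw records, which no section states and which Sections 7 and 8.5 do not favour. Even then, a true dose 2 becomes a 3rd dose only if it falls more than 21 days after the repeat; otherwise it is lost. Nor does the person leave the study: multiple entries are allowed, so that dose entry is what fails.

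The anchor problem survives the reply. The repeats-first reading still counts the gap from any earlier record, so it still drops the day-25 dose and moves later doses down. Nor is this simply detail left for later: the protocol fills in the cell, defines it, and notes that such choices affect which person-time is included.

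**Conclusion.** The point holds in a limited form. Table 4 and the stated purpose of the gap conflict. As written, a genuine dose within 21 days of a repeat record is excluded from its dose cohort even when it is more than 21 days after the previous true dose. This follows from the wording in Sections 7 and 8.5 and Table 4, whichever way doses are numbered. The direction of any later misnumbering depends on a numbering order that the protocol does not give.

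In the sequences tested, the loss of dose 2 is confined to short intervals: 14 of 20 lags at 28 days, none at 42 days or more. At those longer intervals, applying the gap before numbering gives correct labels, while numbering raw records still leaves the repeat in the 2nd-dose position. The lag counts describe possible repeat days, not how often repeats occur. No repeat-record rate is given, and Table 1 gives vaccine counts by brand rather than by dose. Any percentage for lost or mixed doses would therefore rest on invented inputs, and none is offered.

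**What to change.** 1. In the cohort 5 row of Table 4, change the order of application to *before*.
2. Add a sentence to Section 8.5: repeats are collapsed first, keeping the earliest record and dropping any later record that falls inside the protocol's minimum gap from the last retained dose; the retained records are then numbered as doses 1 to 4, and the other exclusions follow.
3. Bring the wording in Section 7 into line, and use the same collapsed sequence wherever a prior dose count is used.
4. State whether a record exactly 21 days after the last retained dose is inside the gap, since the inclusive window and the schedule-based reason for the 21 days need to be reconciled.

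The cost is one table cell, one or two sentences and a change of order in the cohort code, which Section 5 lists as still to be created. No new data are needed. Reporting the number of collapsed records per database would supply the missing rate.
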